4.1.3 Primary Outcome Variable

iFABP concentration.

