5.4 Study Schedule/Study Visits

1. Remote Screening and Invitation to Participate (estimated time = 20 minutes)
2. Informed Consent and First Visit (estimated time = 3 hours)
3. Second Visit (estimated time = 3 hours)

Reminder text and/or telephone messages will be sent the day before and a phone call will be made the morning of the scheduled first and second visits.

During the 28-days study duration, the participants will receive daily phone calls or text, as reminders for the daily pill's intake. They also will be asked to fill out a weekly pill's intake report (Appendix 1) and send a picture of the filled report every 7 days to via e-mail or text message to the researcher contact.

Refer to Schedule of Activities (Appendix 1) and Study Schema (Appendix 1) for the detailed information.

Biospecimens:

40mL of blood will be collected by phlebotomy at the first and second visit. Plasma, peripheral blood mononuclear cells and serum will be separated either from EDTA, heparin or preservative free tubes. Roughly 300 microliters of whole blood will be taken out from the EDTA tubes, and used to measure Phosphatidylethanol (PEth). Peth is direct alcohol biomarker which is found in human blood following alcohol consumption.

Standard Operating Procedures (SOPs): Detailed guidance on study procedures can be found in specific SOPs. See the following documents in the appendix:

- SOP_Blood Processing_2023

Survey / Questionnaire Forms are in the appendix.

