5.5 Statistical Method

The data obtained will be analyzed using R and SAS software. After performing normality tests, we will compare group changes in each biomarker according to the most appropriate statistical test: either t-test (normal distribution) or Wilcoxon-Mann-Whitney (non-normal distribution). Multivariate methods will be applied to verify the relationship between BSE supplementation and gut leak, BSE supplementation and inflammation and BSE supplementation and oxidative stress. The data will be adjusted for following confounders: sex, age, BMI, race/ethnicity and substance use.

Scientific Rigor: The principal investigator (PI) will be blinded for the randomization; the pill bottles will be labeled as "Tablets A" or "Tablets B" by the manufacturer. The PI will be responsible for the data collection's quality control, as well as the experiments execution, assuring proper negative and positive controls and appropriate replicates within experiments. All the findings of the present research will be analyzed and reported with full transparency. The product's manufacturer will not have any authority over the study design, results or scientific publication.

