5.5.1 Sample Size Consideration

The sample size was calculated using the preliminary data for gut leak, the estimated number of participants was 13 (power= 0.8; alpha= 0.05; beta= 0.02). However, to increase the power in transitioning to humans, we plan to recruit 20 subjects for each group. In total, 40 participants will be recruited by convenience by printed advertising, post in social media and word of mouth.

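### Neither the unadjusted test nor the five-factor adjusted analysis is named as primary for iFABP, and the adjustment list leaves out baseline iFABP and does not name baseline PEth

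*Combined protocol and SAP*

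**What the plan says.** The primary outcome variable in section 4.1.3 is "iFABP concentration", with no analysis attached to it.

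Section 5.5 describes two analyses. The first follows normality testing: "we will compare group changes in each biomarker according to the most appropriate statistical test", meaning a t-test or a Wilcoxon-Mann-Whitney test. The second is given as "Multivariate methods will be applied to verify the relationship between BSE supplementation and gut leak", with parallel statements for inflammation and oxidative stress, and then "The data will be adjusted for following confounders: sex, age, BMI, race/ethnicity and substance use". The model form, the outcome scale, the coding of the categorical factors and the meaning of substance use are not stated. Section 5.5.2, headed Planned Analysis, describes the expected contribution of the study but no analysis.

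Section 5.4 has blood drawn at both visits and adds: "Roughly 300 microliters of whole blood will be taken out from the EDTA tubes, and used to measure Phosphatidylethanol (PEth". PEth does not appear in section 5.5. Baseline iFABP is not in the adjustment list; it enters only because the unadjusted test is on change.

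Section 5.5.1 states "we plan to recruit 20 subjects for each group", 40 in all.

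**The concern.** With no primary analysis named, the trial can produce two p-values for its one primary outcome, and nothing in the plan says which counts. Each test may be valid alone, but the freedom to report the better one is not.

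The choice of covariates is a second matter. In a randomised trial, covariates earn their place by predicting the outcome, since confounding at baseline is only by chance. The baseline value of the outcome is the natural first candidate, and it is missing from the list. PEth is an objective measure of the exposure that the protocol holds responsible for gut leak, and it is not named. The five factors that are named use several degrees of freedom in a trial of 40, with no stated reason to expect them to predict change in iFABP.

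**Working it through.** **The plan's own figure.** Section 5.5.1 says "The sample size was calculated using the preliminary data for gut leak" and "the estimated number of participants was 13 (power= 0.8; alpha= 0.05; beta= 0.02". No effect size or SD is given, so the 13 cannot be reproduced. It can only be inverted. If it means 13 per arm, two-sided, at 80% power, then d = (1.960 + 0.842) × √(2/13) = 1.10, or 1.145 by the noncentral t. The stated power and beta also disagree, since power 0.8 means beta 0.20.

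**Inputs.** From the documents: 20 per arm and alpha 0.05. Assumed: a two-sided test; k = 5 covariate degrees of freedom (one per factor) to k = 10 (several levels for the categorical factors); and R², the share of residual variance that the covariates explain, set at 0 or 0.3.

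**1. Choice between two analyses.** I simulated 20,000 trials per setting with no treatment effect, 40 participants, k = 5 or 10 and R² from 0 to 0.5. Each test alone rejected in about 5%. Counting a trial as positive if either test rejected gave 6.7% to 9.1%. Further simulations under other assumptions gave about 6% to 8%. The added choice between t-test and Wilcoxon is not counted.

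**2. Cost of the five factors.** With N = 40 the residual df are 38 − k: 33 for k = 5 and 28 for k = 10. Chance imbalance inflates the variance of the treatment effect by about 37/(37 − k):

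- k = 5: 37/32 = 1.16; break-even R² = 5/37 = 13.5%.
- k = 10: 37/27 = 1.37; break-even R² = 10/37 = 27.0%.

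Allowing also for the lost df, the power break-even is 14% to 28%. Power is from the noncentral t with noncentrality d × √(20/2) / √[(37/(37 − k)) × (1 − R²)]:

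| True d | Unadjusted | k = 5 to 10, R² = 0 | k = 5 to 10, R² = 0.3 |
|---|---|---|---|
| 0.91 | 80% | 74% to 66% | 87% to 81% |
| 1.145 | 94% | 90% to 85% | 97% to 95% |

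If only 32 were analysed (an assumed 20% loss), break-even R² would be 5/29 = 17% to 10/29 = 34%. Power at d = 1.145 and R² = 0 would fall from 88% unadjusted to 81% to 70%.

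**3. Baseline iFABP as a covariate.** Let ρ be the baseline to day-28 correlation, with equal variances. The variance of the treatment effect is proportional to 2(1 − ρ) for change scores and to 1 − ρ² for ANCOVA, a ratio of (1 + ρ)/2 in favour of ANCOVA. At an assumed ρ = 0.5 this is 0.75. With 20 per arm, an effect that ANCOVA detects with 80% power is detected by the change-score t-test with about 70%.

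**4. Baseline PEth as a second covariate.** Break-even for the one extra df is 1/36 = 2.8% of what remains after baseline iFABP. If PEth predicts nothing, the loss is about 1 to 2 points of power.

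**The case against.** The strongest reply is that the adjusted model is sound. A reader might infer that five factors overload a 40-person model. The documents do not support that: for a continuous outcome 28 to 33 residual df remain, the type I error stays near 5%, and the factors raise power if they predict well enough. The loss to 66% needs both the heaviest coding assumed here and covariates that explain nothing; the documents give neither coding nor R². This stands, and limits the covariate point to one of efficiency.

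A reader might also infer that the plan discards a strong predictor in PEth. No figure in the documents links PEth to iFABP, and the drinking threshold for entry could weaken any association. Undefined substance use might even include alcohol. All one can say is that PEth is not named.

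Nor do the documents show that a Visit 2 covariate would be used. Section 5.5 is silent on timing, and appendices not available here may settle it.

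Finally, the multivariable statement is about gut leak, which the primary objective assesses with three markers, so it might not be a second test of iFABP alone. That is possible. But iFABP is the primary outcome and one of the three, and nothing excludes it. The statement needs clarifying on either reading.

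Naming either existing analysis as primary would cure the selection problem. That is also true; the case for ANCOVA rests on precision.

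**Conclusion.** The point holds in a limited form. The plan names a primary variable but no primary analysis, and free choice between its two analyses raises the two-sided error from 5% to about 6% to 9%. That is modest, and this is a declared pilot, but it is avoidable.

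The effect of the five factors on precision cannot be determined from the documents: on the stated assumptions, power of 80% could fall to 66% or rise to 87%. Baseline iFABP has the clearer claim to a place in the model. Its gain depends on ρ, which is not given, and shrinks as ρ approaches 1. Baseline PEth is a low-cost option with no documented benefit. Effect sizes, R², ρ, the covariate coding and the 20% loss are all assumptions. This is an improvement to be had from data already planned; it does not show that the adjusted analysis is invalid.

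**What to change.** In section 5.5 or 5.5.2:

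- Name one primary analysis: ANCOVA of day-28 iFABP on treatment and baseline iFABP, on the log scale if the values are skewed, with the rule for that decision written down before unblinding.
- Decide in advance whether baseline PEth enters as a second covariate, at a cost of one df. It should not simply be added to the five factors, which would increase the df cost.
- Make the unadjusted test and the five-factor model sensitivity analyses. State the model form and coding, define substance use, and use Visit 1 values only.
- Do not adjust for Visit 2 PEth, which is measured after randomisation. Report the between-arm difference in PEth change descriptively, to show whether drinking changed differently.

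The cost is a change of wording; no new sample, assay or participant is needed. The downside is that the five-covariate result becomes secondary.

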4.1 General Design Description

This will be a prospective, randomized, double-blind placebo-controlled clinical pilot study. The participants will be recruited by convenience by printed advertising and word of mouth.

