5.2 Data Collection

We will use the REDCap (Research Electronic Data Capture) software toolset and workflow methodology designed for building and managing online surveys and databases to allow electronic data collection from multi-site clinical research studies. Data will be collected by interview and observer-assessments, and multiple levels of quality control will be used to ensure the highest level of data quality and security. The REDCap system allows for restricted access, read-and-write privileges for each database and data entry form. Routine data quality reports are produced evaluating range checks, valid fields, and missing fields. All changes to the database are logged and time stamped. In our prior work, the error rate was <1%. The participants will be randomized into placebo or BSE supplementation group, blood samples and data will be collected in two time-points, baseline day zero of treatment (Visit 1) and after 28 days of treatment (Visit 2). For the supplementation, the participants will be advised to take 2 capsules per day of the AVMACOL® (Nutramax Laboratories) supplement for a 28-days period. The placebo group will receive capsules with no BSE and will be instructed to take 2 capsules per day for the 28-days period.

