5.4.4 Monitoring plan for pills intake adherence

The participants will receive daily text messages as a reminder to take the pills and will be asked to confirm when the pills were already taken. Also, they will be given a weekly pill's intake report document (please, see on Appendix 1), and asked to send a picture of the filled document every 7 days. Finally, the participants will be asked to bring the tablets container back by the end of the study (Full test visit 2) and the pills left will be counted by the researcher¹⁴. The compliance to the intervention's schedule needs to reach 80% of the total 28 days, meaning that if the enrolled subject did not take the pills for more than 5 days they are going to be considered as drop out.

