6.10 Study Monitoring

Ensuring adherence to IRB approved procedures in the study is the responsibility of the Principal Investigator. Once a week the PI will review the accuracy of the data collected and the protocol compliance.

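### One bottle code per arm means a single code break decodes all 40 assignments; unique kit numbers would limit it to 1 of 40

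*Combined protocol and SAP*

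**What the plan says.** Section 4.1 sets the masking level: "This will be a prospective, randomized, double-blind placebo-controlled clinical pilot study". Section 5.5 gives the method. It says "The principal investigator (PI) will be blinded for the randomization" and that "the pill bottles will be labeled as 'Tablets A' or 'Tablets B' by the manufacturer". Section 5.5.1 gives the group size: "we plan to recruit 20 subjects for each group".

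Two kinds of contact with the product or the data matter here.

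- **Pill count.** Under section 5.4.4 participants bring the container back at visit 2, and "the pills left will be counted by the researcher". The same section classes a participant as a drop-out when more than 5 of the 28 days are missed (80% compliance).
- **The PI's duties.** Section 5.5 makes the PI responsible for quality control of data collection, "as well as the experiments execution, assuring proper negative and positive controls". Section 6.10 adds: "Once a week the PI will review the accuracy of the data collected and the protocol compliance".

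Sections 6.3 and 6.8 identify research data and biological samples by study ID. Section 5.2 notes that the database can restrict access form by form.

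The supplied text does not say who generates the randomisation list, who holds the A/B key, how one participant would be unblinded, or when the key is opened. The PI is the only role named as blinded.

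**The concern.** A two-letter code labels the group, not the participant. Everyone on A shares an arm, and so does everyone on B. This has two consequences.

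First, no single participant can be unblinded alone. Once one letter is decoded, the other follows.

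Second, anyone who sees the letters can group participants by arm before knowing which arm is which, and can then pool impressions across people. Section 2.3 lists diarrhoea and other gastrointestinal intolerance among the risks of taking the pills, so such impressions could arise. The documents give no rates by arm.

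What is at stake is the set of decisions that still involve judgement:

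- the investigator's causality grading of adverse events (section 5.3);
- repeats and quality control of assays;
- the handling of out-of-range values (section 6.5);
- who counts as a drop-out when the daily messages, weekly report and pill count disagree. Section 5.4.4 lists all three without saying which prevails.

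If the letter reaches the person deciding, these choices can be made knowing who shares an arm and, after one break, which arm it is.

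**Working it through.** **Inputs.** Two codes, one per arm (section 5.5). Twenty participants per group (section 5.5.1). A total of 40 (sections 4.1.6 and 5.5.1).

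**Plan's own figure.** 20 × 2 = 40, which agrees with the stated total.

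**Assignments revealed by one code break.** Direct exposure is 40 divided by the number of codes, for someone who knows which code each participant has.

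- As written, 2 codes: 40 / 2 = 20 directly. The other letter can only be the other arm, so the remaining 20 follow. Total 40 of 40.
- Four codes, two per arm (illustration only): 40 / 4 = 10 of 40 directly.
- A unique number per participant: 40 / 40 = 1 of 40. If allocation is exactly 20:20, each other participant then has a chance of 19/39 = 0.49 of being in the revealed arm, so almost nothing is learned about them.

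**Where the letter travels.** Setting the sections side by side:

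- *Container.* The bottle is labelled A or B (section 5.5), is returned and is counted by the researcher (section 5.4.4). No relabelling is described, so it is a fair inference that the counter sees the letter. The count is one input to the compliance rule: 28 × 0.80 = 22.4 days, so 6 missed days gives 22/28 = 78.6% and drop-out.
- *Samples and data.* These carry a study ID (sections 6.3 and 6.8). No section puts the letter on a tube or in a data file.
- *PI.* The same person covers experiments, quality control (section 5.5) and the weekly compliance review (section 6.10). No section says the letter is kept from this person.

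**Pooling of weak cues (illustration; accuracy and independence assumed).** Suppose each participant's cues point to the correct arm with probability p, independently, and an observer takes the majority over 40 participants grouped by letter. The probability of naming the letters correctly is P(X ≥ 21) + ½ P(X = 20), with X binomial (40, p):

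| Assumed p | Probability of naming the letters correctly |
|---|---|
| 0.50 | 0.50 |
| 0.55 | 0.74 |
| 0.60 | 0.90 |
| 0.70 | 0.996 |

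The documents give no value for p. The table shows only what a shared code makes possible. Unique numbers remove the grouping that pooling needs.

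**The case against.** The strongest case against is that the plan already limits the damage. Samples and data carry study IDs, the database can restrict access, the outcomes in sections 4.1.3 and 4.1.4 are laboratory measures, reminders go to every participant daily, and the drop-out rule is numeric. Coding by the manufacturer is a weak mask, but it is a mask. Section 5.5 does not say the bottle carries nothing besides the letter. The appendices and the blood-processing procedure are not in the text supplied, so its silence on handling is limited evidence.

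Most of this stands, and it rules out several stronger readings that a reader might infer.

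- *Assays and data review are done with the letter in view.* The study-ID provisions in sections 6.3 and 6.8 point the other way. The supported statement is only that the plan does not say the letter is withheld from the PI.
- *Blinded staff count the pills.* Section 5.4.4 says the researcher does so. It does not say whether that person is blinded or is the PI.
- *A correct guess unblinds the trial.* A guess does not confirm itself, and a single guess is right half the time by chance.
- *The two arms differ in dosage form.* Sections 5.4.4 and 5.5 speak of tablets, but section 5.2 uses capsules for both arms, including "The placebo group will receive capsules with no BSE". The wording is inconsistent across sections and does not show a mismatch between arms.
- *The product is recognisable.* Nothing describes the look, smell or taste of either product.

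None of this changes the labelling itself. A study ID on the tube does not stop one decoded letter from decoding every bottle that carries a letter.

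**Conclusion.** The point holds as a weakness in a stated design choice. The trial's only described masking device is an arm-level code. One code break therefore exposes 40 of 40 assignments, against 1 of 40 with unique kit numbers.

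The 40 is a worst case. It applies to a person who has both the meaning of a letter and the list of participants' letters, and it assumes the planned 20 per group are enrolled. How likely a break is cannot be judged from the documents.

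A reader might conclude that the double-blind claim is already untenable. The documents do not support that: they show a fragile blind with no described key-holder or per-participant code break, not a failed one. The change should be made because it is cheap and protects the judgement-based decisions.

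**What to change.** In section 5.5, replace the A/B labelling with a unique kit number on each bottle (e.g. 001 to 040), applied by the manufacturer from a concealed randomisation list, with no code shared across participants. State that the manufacturer, or another existing party outside the study team, holds the key. State that it is opened for a single participant only if needed, and otherwise after database lock. With no shared letter, the returned container no longer tells the pill counter or the PI who is in the same arm.

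Separately, reconcile the capsule and tablet wording in section 5.2 with sections 5.4.4 and 5.5, and state whether the two products match in form and appearance.

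The cost is some relabelling and the keeping of a numbered list linked to study IDs. It should be small because the manufacturer already labels the bottles, although the documents give no terms for that work. Sample size, visits and assays are unaffected.

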5.5.1 Sample Size Consideration

The sample size was calculated using the preliminary data for gut leak, the estimated number of participants was 13 (power= 0.8; alpha= 0.05; beta= 0.02). However, to increase the power in transitioning to humans, we plan to recruit 20 subjects for each group. In total, 40 participants will be recruited by convenience by printed advertising, post in social media and word of mouth.

5.5.2 Planned Analysis

The present study will allow us to collect important data and shed light on BSE diet supplementation as an adjuvant to reduce gut leak, decrease inflammation and improve the antioxidant status. Furthermore, the published results from this clinical study will contribute to the scientific literature by supporting the feasibility of cost-effective and simple interventions for a complex issue in alcohol using patients.

6. Trial Administration

6.1 Ethical Considerations: Informed Consent

Consent forms will be Institutional Review Board (IRB)-approved and the participant/legally authorized representative (LAR) will be asked to read and review the document. The PI will explain the research study to the participant and answer any questions that may arise. This conversation will take place in a private room. Participants/LAR will have the opportunity to carefully review the written consent form and ask questions prior to signing. The participants/LAR should have the opportunity to discuss the study with their family or surrogates or think about it prior to agreeing to participate. The participant will sign the informed consent document prior to any procedures being done specifically for the study. Participants/LAR must be informed that participation is voluntary and that they may withdraw from the study at any time, without prejudice. A copy of the informed consent document will be given to the participants/LAR for their records.

